3.4. Randomization and Treatment Assignment

3.4.1. Randomization

Approximately 340 subjects will be randomized 1:1 to receive either pamrevlumab or placebo, resulting in approximately 170 subjects per treatment arm. Each subject will receive a unique study ID number during screening.

Subjects will be stratified at randomization according to GAP stages (I, II, III), derived from the GAP score obtained during screening (See [Section 6.2.5](#) and [Appendix 5](#)). Automated randomization and treatment assignments will be performed by an Interactive Response System (IXRS or IRT).

3.4.2. Treatment Assignment

Subjects will be randomized 1:1 to one of two treatment arms:

Arm A: Pamrevlumab

Arm B: Placebo

3.5. Blinding

This is a double-blind, placebo-controlled study. The Investigator, study site staff, subjects, selected Sponsor clinical team and designees are blinded to study drug assignment. Blinded treatment with a placebo control is the gold standard method for obtaining unbiased assessments of safety and efficacy in clinical trials of investigational drugs such as pamrevlumab.

3.5.1. Maintenance of Blinding

The study blind will be maintained for all parties specified above throughout the study with the exception of the scenarios outlined in Section 3.5.2. Pamrevlumab and placebo are identical in appearance, packaging, and labeling in order to maintain the study blind.

3.5.2. Request for Unblinding of Treatment Assignment

Breaking the blind during the study (for a single subject) should be considered only when knowledge of the treatment assignment is deemed essential by the Investigator due to immediate safety concerns, or is considered essential for the immediate subject management. The responsibility to break the blind (for a single subject) in emergency situations resides solely with the Investigator. It is the Investigator's responsibility to promptly document and explain any unblinding to the Sponsor.

Such emergency unblinding will be done by the Investigator using the automated Interactive Response System (IXRS or IRT) which ensures rapid unblinding in emergency situations.

4. SELECTION AND WITHDRAWAL OF SUBJECTS

4.1. Subject Inclusion Criteria

In order to be eligible for inclusion in this trial, a subject must meet all of the following:

1. Age 40 to 85 years, inclusive, at screening initiation.
2. Diagnosis of IPF as defined by ATS/ERS/JRS/ALAT guidelines (Raghu 2018).
3. IPF diagnosis within the past 7 years, with onset defined as the date of the first recorded diagnosis of IPF by HRCT and/or surgical lung biopsy (SLB), or other appropriate tissue sample (e.g., cryobiopsy) in the medical history.
4. Interstitial pulmonary fibrosis defined by HRCT scan at screening, with evidence of $\geq 10\%$ to $< 50\%$ parenchymal fibrosis (reticulation) and $< 25\%$ honeycombing, within the whole lung. **NOTE:** this requires confirmation by an Independent Radiology Imaging Review Group, prior to randomization. If a recent HRCT scan (within 3 months prior to screening) is available, it can be utilized for screening purposes, provided it is submitted and evaluated by the Independent Radiology Imaging Review Group, is adhering to the same imaging acquisition parameters detailed in the Imaging Core Manual (ICM), and is either using the same accredited scanner, or is performed using the same modality, as the on-study HRCT scans.
5. FVCpp value $> 45\%$ and $< 95\%$ at Screening and Day 1 (prior to randomization).
6. Diffusing capacity of the lungs for carbon monoxide (DLCO) percent predicted and corrected by Hb value $\geq 25\%$ and $\leq 90\%$ at screening (determined locally). If a DLCO is available within 3 months prior to screening, it can be utilized for screening purposes.
7. Both FVC and DLCO testing must be representative of the IPF underlying disease (i.e. have been obtained in absence of an acute respiratory event [e.g. lung infection, cold] or other events that are known to affect PFT testing results [e.g., broken rib, chest pain, other]).
8. Previously treated with an approved IPF therapy (i.e., pirfenidone or nintedanib) but discontinued at least 1 week prior to screening, unless neither treatment is available in the host country. **NOTE:** no subject should discontinue approved therapy for the purpose of enrolling in this study.

9. Male subjects with partners of childbearing potential and female subjects of childbearing potential (including those <1 year postmenopausal) must use a highly effective method of contraception per Clinical Trial Facilitation Group (CTFG) recommendation (see protocol section 5.2.3 for details) during the conduct of the study, and for 3 months after the last dose of study drug. Women not of childbearing potential are defined as:
 - a. Post-menopausal; women (defined as at least 12 months with no menses without an alternative medical cause); in women < 45 years of age, a high follicle stimulating hormone (FSH) level in the post-menopausal range may be used to confirm a post-menopausal state in women not using hormonal contraception or hormonal replacement therapy. OR
 - b. Have had a hysterectomy and/or bilateral oophorectomy, bilateral salpingectomy or bilateral tubal ligation/occlusion, at least 6 weeks prior to screening; OR
 - c. Have a congenital or acquired condition that prevents childbearing.
10. Able to understand and sign a written informed consent form.

4.2. Subject Exclusion Criteria

Subjects will be ineligible for and excluded from this trial if any of the following apply:

1. Previous exposure to pamrevlumab.
2. Evidence of significant obstructive lung disease by any of the following criteria: (1) forced expiratory volume in 1 second/forced vital capacity (FEV1/FVC) ratio <0.70, or (2) extent of emphysema greater than the extent of fibrosis on HRCT. **NOTE:** this requires confirmation by an Independent Radiology Imaging Review Group, prior to randomization.
3. Female subjects who are pregnant or nursing.
4. Smoking within 3 months of screening and/or unwilling to avoid smoking throughout the study.
5. Interstitial lung disease (ILD) other than IPF, including but not limited to any of the other types of idiopathic interstitial pneumonias; lung diseases related to exposure to fibrogenic agents or other environmental toxins or drugs; other types of occupational lung diseases; granulomatous lung diseases; pulmonary vascular diseases; systemic diseases, including vasculitis, infectious diseases and connective tissue diseases. In cases of uncertain diagnosis, serological testing and/or review by multi-disciplinary team should be performed to confirm diagnosis of IPF vs. other types of ILD.
6. Sustained improvement in the severity of IPF during the 12 months prior to screening, based on changes in FVC, DLCO, and/or HRCT scans of the chest.
7. History of other types of respiratory diseases, including diseases or disorders of the airways, lung parenchyma, pleural space, mediastinum, diaphragm, or chest wall that, in the opinion of the Investigator, would impact the primary protocol endpoint or otherwise preclude the subject's participation in the study.

8. Medical conditions (e.g. MI/stroke within the past 6 month), or logistical challenges that in the opinion of the Investigator preclude the subject's adequate participation in the study.
9. Poorly controlled chronic heart failure (NYHA Class 3 or above); clinical diagnosis of cor pulmonale requiring specific treatment; or severe pulmonary arterial hypertension requiring specific treatment that, in the opinion of the Investigator, would preclude the subject's participation in the study.
10. Clinically important abnormal laboratory tests (including serum creatinine ≥ 1.5 x upper limit of normal [ULN], hemoglobin (Hb) < 10 g/dL, white blood cells $< 3,000/\text{mm}^3$, platelets less than $100,000/\text{mm}^3$, serum total bilirubin > 1.5 x ULN, serum alanine aminotransferase (ALT) or aspartate aminotransferase (AST) ≥ 2 x ULN, or serum alkaline phosphatase ≥ 2 x ULN).
11. Ongoing acute IPF exacerbation, or suspicion of such process during screening or randomization, including hospitalization due to acute IPF exacerbation within 4 weeks prior to or during screening.
12. High likelihood of lung transplantation (in the opinion of the Investigator) within 6 months after Day 1.
13. Use of any investigational drugs or unapproved therapies, or participation in any clinical trial with an investigational new drug within 30 days prior to screening.
14. Daily use of PDE-5 inhibitor drugs (e.g. sildenafil, tadalafil), except for treatment of severe pulmonary artery hypertension.
15. Any current malignancy (this does not include localized cancer such as basal or squamous cell carcinoma of skin). Any history of malignancy likely to result in mortality, or requiring significant medical or surgical intervention within the next year.
16. History of allergic or anaphylactic reaction to human, humanized, chimeric or murine monoclonal antibodies, or to any component of the excipient.
17. Any condition (other than IPF) that is likely to result in the death of the patient within the next year.
18. Acute infection requiring any of the following:
 - a. Hospital admission for ≥ 24 hours within four weeks prior to screening, or during screening
 - b. Treatment with antibiotics (IV, IM, oral, or inhaled) within four weeks prior to screening, or during screening
 - c. Active or recent (≤ 4 weeks prior to randomization) upper or lower respiratory tract infection
 - d. Active tuberculosis requiring treatment within 12 months prior to screening
19. Known history of immunodeficiency, including but not limited to HIV infection
20. Receipt of a live/attenuated vaccine within the four weeks prior to randomization

21. Chronic treatment with any of the following within four weeks or five half-lives (whichever is longer) prior to randomization, if used to treat IPF:
 - a. Immunosuppressive or immunomodulatory therapies (e.g., azathioprine, cyclosporine A, cyclophosphamide, D-penicillamine, interferon-gamma, tumor necrosis factor- α antagonists)
 - b. Cytotoxic drugs (e.g., colchicine)
22. The Investigator judges that the subject will be unable to fully participate in the study and complete it for any reason, including inability to comply with study procedures and treatment, addiction, or any other relevant medical or psychiatric conditions.
23. Country Specific Criteria (Czech Republic Only): Positive result from a Tuberculosis (TB) screening test performed within 6 months prior to screening for the study. TB testing may be done locally.

4.3. Subject Study Withdrawal Criteria

Subjects who do not receive all study drug doses in the main study are encouraged to remain in the study and continue with the regular study visits and assessments. However, subjects may withdraw from the study at any time, for any reason. Reasons for discontinuing study drug treatment, as well as reasons for withdrawing from study, will be captured on CRF.

Mandatory reasons for withdrawing the subject from the study include the following:

- Any safety concern in the Investigator's opinion, that precludes further study participation, including infusion-associated reactions deemed life-threatening by the Investigator (see also/ Section 5.1.6)
- Lung transplant
- Pregnancy
- Major protocol deviation that substantially affects subject safety or assessment of efficacy endpoints
- Withdrawal of Consent

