Subjects who were previously treated with approved IPF therapies (i.e., nintedanib or pirfenidone; unless neither treatment is available in the host country) may be eligible for screening, provided that the subject is not currently receiving treatment with an approved IPF therapy.

NOTE: No subject should discontinue an approved IPF therapy for the purpose of enrolling in this study.

Approximately 340 eligible subjects will be randomized at a 1:1 ratio to Arm A or Arm B, respectively:

Arm A: pamrevlumab, 30 mg/kg IV, Day 1 and every 3 weeks thereafter

Arm B: Matching placebo IV, Day 1 and every 3 weeks thereafter

Randomization will be stratified by GAP stage (I, II, III) derived from the GAP score obtained during screening (See Appendix 5). **NOTE:** For calculation of the GAP score: Use the Best-Test Review (BTR) assessment provided by the spirometry vendor over-reader of the screening value (see Section 6.2.5 and Appendix 5).

The intent of this study is to evaluate the efficacy and safety profile of pamrevlumab as monotherapy in subjects with IPF who were previously treated with an approved therapy but who discontinued that therapy (possible reasons for discontinuation of approved therapy could include, but are not limited to, intolerance or disease progression), unless neither treatment is available in the host country.

During the treatment period, co-administration of an approved IPF therapy (i.e., pirfenidone or nintedanib) is acceptable if clinically indicated in the Investigator's opinion, after assessment of potential risks/benefits of such combination with blinded study treatment. However, since subjects either tried and stopped treatment with an approved IPF therapy, or have no such treatment available, it is not expected that many subjects will resume treatment with an approved IPF therapy during this study.

Subjects who complete the Week 48 visit of the main study (regardless of the number of study drug infusions received) will be eligible to participate in the optional open-label extension (OLE) phase of the study that offers continuing access to pamrevlumab regardless of randomization assignment in the main study. Details of this OLE phase are outlined in Appendix 6.

Subjects who discontinue study treatment for any reason should be encouraged to remain in the study and be followed for all study visits and assessments.

The following assessments will be assessed centrally:

- Pulmonary function tests (PFTs)

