3.3.1. Study Duration

Subjects are encouraged to receive all 17 study drug doses in the main study. Subjects who do not receive all doses are encouraged to continue with study visits and assessments.

Subjects who complete the Week 48 visit (regardless of the number of study drug doses received) will be eligible for an open-label, extension (OLE) phase, which will provide continuing access to pamrevlumab until the last subject completes 48 weeks of treatment in the OLE phase, or pamrevlumab is commercially available for the indication of IPF, or the Sponsor decides to end the OLE phase, whichever occurs first.

Subjects who withdraw from the main study early, for any reason, will have an Early Study Termination visit (ET) as soon as feasible. Study procedures to be performed during the ET visit can be found in the SOA (Appendix 1). These subjects will also have a safety follow up visit 28 days after the last dose, with a follow-up phone call 60 days after the last dose for a final safety assessment. Such subjects should also be contacted by phone at weeks 24 and 48 to check the subject's vital status. These subjects will not be eligible for the OLE phase

See also Section 4.3 for mandatory Study Withdrawal reasons, and Section 4.4 for procedures related to Early Study Withdrawal.

Figure 1: FGCL-3019-095 Study Schema

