4.4. Subject Study Withdrawal Procedures/Assessments

Subjects who terminate / withdraw from the study early, for any reason, will have an Early Study Termination (ET) visit as soon as feasible. Study procedures to be performed during the ET visit can be found in the SOA (Appendix 1). At the ET visit, PFTs and questionnaires do not have to be repeated, if the last one (excluding screening visit) was performed within 8 weeks of this visit; HRCT does not have to be repeated, if the last one (excluding the screening visit) was performed within 4 months of this visit.

These subjects will have a safety follow-up visit 28 days after the last dose. A follow-up phone call 60 days after last dose will also be completed for a final assessment of safety.

In addition, these subjects should be contacted by phone for vital status at weeks 24 and 48. These subjects will not be eligible for the OLE phase.

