The Investigator or other qualified personnel must be either present, or immediately available, during all infusions and observation periods for each subject. If a subject has a significant infusion associated AE, the infusion rate may be slowed or temporarily stopped, depending on the severity of symptoms. If such a subject continues study drug dosing, a physician should be immediately available during all subsequent infusions and observation periods at the site.

Subjects who experience an infusion associated AE will not be allowed to participate in Home Health Care (HHC). In addition, if a subject experiences a life-threatening (per Section 7.3.3) infusion-associated AE, study drug treatment must be permanently discontinued (see [Section 4.3](#)).

The Investigator has the option to use premedication, e.g., antihistamines, nonsteroidal anti-inflammatory drugs (NSAIDs) for a subsequent infusion: this may be discussed with the FibroGen Medical Monitor or designee.

Infusions are to be continued until the total volume has been administered. Subjects will remain at the study site for 1 hour (2 hours for Czech Republic Only) after the end of the infusion for clinical observation. This post-infusion observation period may be reduced to 30 minutes if the subject has had no infusion-associated AEs during the first three infusions.

Study drug will be administered at a hospital or ambulatory setting with adequate facilities for managing medical emergencies. Medications for the treatment of acute reactions, including anaphylaxis, must be available to study site staff for immediate use. There is no specific treatment for a pamrevlumab overdose or infusion-associated AEs. Signs and symptoms should be managed with appropriate standard of care treatment.

The Sponsor may consider the use of properly trained home health care staff to administer the infusions of study drugs at the subject's home and corresponding study assessments during the conduct of the study (after the completion of at least three 30-minute infusions without safety concerns), consistent with institutional regulations and policies. See Section 5.1.7 for details.

COVID-19 Vaccine and Study Drug Administration

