NOTE: In accordance with FDA/EMA Guidance: During the COVID-19 pandemic, the visit modality (e.g.: in-person versus remotely) and scheduling maybe adjusted and conducted at the discretion of the Investigator, in accordance with the site's rules and recommendations, and using all necessary precautions. If a visit has to be done remotely, it can be conducted with any technology available to the site and study subjects.

Unscheduled Visits

Unscheduled visits/assessments will be captured accordingly in the clinical database

Subject Study Withdrawal Criteria

Subjects may withdraw from the OLE at any time, for any reason. Such subjects will have an early termination visit (EX ET) as soon as feasible. Study procedures to be performed during the EX ET visit can be found in the OLE Schedule of Assessments (SOA) presented in Appendix 6. Reasons for withdrawal will be captured on CRF.

Mandatory reasons for withdrawing from the OLE phase include:

- Any safety concern in the Investigator's opinion, that precludes further study participation
- Lung transplant
- Pregnancy
- Withdrawal of Consent

Safety Follow-Up

All subjects will have two Safety Follow-Up Visits:

- 28 days after the last dose
- 60 days after last dose: follow-up phone call, for a final safety assessment

The visit windows for the safety assessments are: 28 days +7 days and 60 days +7 days (phone call) after the last dose.

See OLE SOA in Appendix 6.

After the protocol-required reporting period (60 days after the last dose), the Investigator does not need to actively monitor subjects for SAEs. However, if the Investigator becomes aware of an SAE/death that may be possibly related to study treatment after the protocol-required reporting period, the Investigator may report the event to FibroGen as outlined in Section 7 of the main study. SAEs reported outside of the protocol-required reporting period will be captured within the safety database only as clinical trial cases for the purposes of expedited reporting.

Study Assessments:

All study assessments are done per the local standard of care with the exception of weight, pre and post infusion vital signs and pregnancy test. Refer to OLE SOA for details.

Vital Signs (including Weight) – Pre and Post pamrevlumab infusion

Vital signs to be collected include heart rate, blood pressure and temperature:

- Heart rate should be collected as beats/min
- Systolic and diastolic blood pressure should be collected from subjects in seated position (mmHg)

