3.4. Study Periods

[figure not shown]
This study consists of the following study periods (Figure 1):

- Main (double-blind, placebo-controlled) study period:
 - Screening period: Up to 6 weeks
 - Treatment period: 48 weeks
- Optional, open label extension (OLE) period:

Access to pamrevlumab during the OLE period will be available until the last enrolled subject completes 48 weeks of treatment in the OLE period, or pamrevlumab is commercially available for the indication of IPF, or the Sponsor decides to end the OLE period, whichever occurs first.

- Follow-up period/final safety assessment:
 - 28 days after the last dose: scheduled visit
 - 60 days after the last dose: follow-up phone call, for a final safety assessment

Figure 1: Study Schema

The intent for this study is to evaluate the efficacy and safety profile of pamrevlumab as monotherapy in subjects with IPF who were previously treated with an approved therapy but

Confidential Page 13 of 56

who discontinued that therapy (possible reasons for discontinuation of approved therapy could include, but are not limited to, intolerance or disease progression), unless neither treatment is available in the host country.

After randomization and during the treatment period, co-administration of an approved IPF therapy (i.e., pirfenidone or nintedanib) is permitted if clinically indicated in the Investigator's opinion, provided that the Investigator assesses the potential risks/benefits of combining approved IPF therapies with blinded study treatment.

Subjects who complete the Week 48 visit of the main study (regardless of the number of study drug infusions received and or treatment group assigned in the double-blind period) will be eligible to participate in the optional OLE period of the study that offers continuing access to pamrevlumab regardless of randomization assignment in the main study.

Subjects who discontinue study treatment for any reason are encouraged to remain in the study and be followed for all study visits and assessments.

The following assessments will be assessed centrally by independent external vendors or study committees:

- Pulmonary function tests (PFTs)
- High-resolution computed tomography (HRCT)
- Acute IPF exacerbations and respiratory hospitalizations

In addition, an independent Data Monitoring Committee (DMC) will review safety data and other clinical data (with the authority to unblind such data) on a periodic basis to monitor overall subject safety.

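### Protocol 4.3 can be read as requiring study withdrawal after a life-threatening infusion reaction, where 5.1.6 requires only that study drug stop; such withdrawal would end scheduled spirometry and HRCT

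*Protocol*

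**What the plan says.** Protocol 4.3 introduces its list with "Mandatory reasons for withdrawing the subject from the study include the following". The first bullet is a safety concern, in the Investigator's opinion, "that precludes further study participation, including infusion-associated reactions deemed life-threatening by the Investigator", and it refers the reader to 5.1.6. Protocol 3.3.1 describes the list in the same terms: "See also Section 4.3 for mandatory Study Withdrawal reasons, and Section 4.4 for procedures related to Early Study Withdrawal".

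Protocol 5.1.6 states one consequence for this event: "if a subject experiences a life-threatening (per Section 7.3.3) infusion-associated AE, study drug treatment must be permanently discontinued". It refers back to 4.3 and does not say whether the subject leaves the study.

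On subjects who are off drug, the Synopsis says: "Subjects who discontinue study treatment for any reason should be encouraged to remain in the study and be followed for all study visits". The double-blind SAP, Section 3.4, agrees: "Subjects who discontinue study treatment for any reason are encouraged to remain in the study and be followed for all study visits and assessments". The opening sentence of Protocol 4.3 gives similar encouragement to subjects who do not receive every dose.

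Under Protocol 4.4 a subject who leaves the study has an early termination (ET) visit, a safety visit 28 days after the last dose, a call at 60 days, and vital-status calls at Weeks 24 and 48. No spirometry or HRCT is scheduled after the ET visit.

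The primary estimand uses a treatment-policy strategy (Protocol 8.3.4.1; double-blind SAP 6.7.1.1.3), and SAP 6.7.1.1.4 brings FVC measured after treatment discontinuation into the primary analysis.

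**The concern.** The two sections attach different follow-up to the same event. They are not logically incompatible, because leaving the study entails stopping drug. But each points to the other and neither settles whether assessments continue.

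A serious reaction to an infusion is a reason to stop infusions. It is not in itself a reason to stop spirometry or HRCT. If a site withdraws the subject, the primary analysis loses the off-drug FVC that the treatment-policy strategy is meant to use and relies on missing at random in its place. Time to disease progression is affected as well, since event-free subjects are censored at their last spirometry (SAP 6.7.2.1.4.1).

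The opposite choice has its own problem. SAP Table 1 counts as a major deviation a subject who met withdrawal criteria and stayed in. A site that follows the Synopsis and retains the subject could be recorded under that heading, subject to the sponsor's medical review.

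**Working it through.** **Reading the text.** In 4.3 the infusion-reaction clause sits inside a bullet conditioned on the Investigator's opinion that participation is precluded. The clause is attached by a word that presents these reactions as instances of the condition being met. A site could therefore read withdrawal as required, or as required only when the Investigator judges it so. The open-label extension (OLE) list in Appendix 6 ("Mandatory reasons for withdrawing from the OLE phase include") has the same safety bullet without the clause. That does not show the clause is an error in the main study, but it shows that the bullet works without it.

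**Reproducing the plan's power.** Inputs from Protocol 8.1: 340 subjects 1:1, difference 120 mL, SD 300 mL, two-sided alpha 0.05, about 20% dropout.
- Evaluable per arm: 170 x 0.8 = 136.
- Two-sample t-test power with 136 per arm: 90.8%. The stated figure of at least 90% is reproduced.
- Design standard error: 300 x sqrt(2/136) = 36.4 mL.

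**How many infusions put the Week 48 value at risk.** Infusion k falls on Day 21(k-1)+1, that is Days 1, 22, ..., 295, 316, 337. The Week 48 spirometry window opens on Day 296 (SAP Appendix 2, Table 7), so 15 of the 17 infusions come before it. Counting all 15 as losing the Week 48 value slightly overstates the loss, because an ET test after the Day 295 infusion could still fall in the window.

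**Assumptions, since the documents give no rate.** A life-threatening reaction occurs in 1-3% of the active arm; reactions are spread evenly over infusions; every affected subject is withdrawn; 80% would otherwise have had a Week 48 value; and the whole 120 mL benefit is lost after the reaction. The last is an upper case, least realistic for late reactions.

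**Bias under missing at random** = rate x 120 x 0.8 x 15/17.
- 1%: 0.01 x 120 x 0.8 x 15/17 = 0.85 mL, and 0.85/36.4 = 2% of the standard error.
- 3%: 0.03 x 120 x 0.8 x 15/17 = 2.54 mL, and 2.54/36.4 = 7% of the standard error.

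If benefit instead builds linearly and what has accrued is kept, the mean fraction still to come over the 15 infusions is 1 - 147/336 = 0.5625. The bias is then 0.48 to 1.43 mL. At a rate of 0.1% the upper-case formula gives 0.08 mL.

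**Power.** Active subjects lost = 170 x rate x 0.8 x 15/17 = 1.2 at 1% and 3.6 at 3%.
- 135 vs 136: 90.7%.
- 132 vs 136: 90.4%.
- If both arms lost 3.6, each would have 136 - 3.6 = 132.4, against the 132.3 per arm that 90% power needs. Power would be 90.0%.
- If these withdrawals fall within the 20% already allowed, power does not change.

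**The case against.** The strongest reply is that the text can be read consistently: drug always stops (5.1.6), and the subject leaves only if the Investigator judges that participation is precluded (4.3). Appendix 6 lends support. It bars from the OLE anyone who had an allergic or anaphylactic reaction to study drug in the main study, yet the OLE is open only to subjects who completed Week 48, so the protocol seems to expect some reactors to get that far. This stands as far as it goes. It rules out saying that a site following 4.3 would necessarily end spirometry. It does not settle life-threatening cases, since milder reactions would explain the OLE exclusion equally well.

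It is also fair to say that the consequences are partly covered. The jump-to-control and tipping-point analyses (SAP 6.7.1.2.2 and 6.7.1.2.3) address missing active-arm values, vital status is still collected by phone, and dropout is budgeted. These analyses model values that could have been measured, but they limit the harm.

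Three stronger readings are tempting and not supported:
- **Losses fall mainly in the active arm.** No document gives infusion-reaction rates by arm. Protocol 2.5 says infusions have been well tolerated. In the placebo-controlled Phase 2 study, fewer pamrevlumab than placebo subjects stopped treatment for a serious treatment-emergent event (3 vs 7; Protocol 2.6.3), though that count is not specific to infusions.
- **The ET waiver makes the loss worse.** Protocol 4.4 says "PFTs and questionnaires do not have to be repeated, if the last one (excluding screening visit) was performed within 8 weeks of this visit". The waiver is optional, and ET spirometry before Day 296 could not be a Week 48 value whether or not it was done.
- **Retained subjects distort the per-protocol analysis.** That set already requires at least 36 weeks of treatment (SAP 5.2.2), so a deviation could change membership only for later reactions.

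**Conclusion.** The concern holds as an ambiguity. Protocol 4.3 can reasonably be read as requiring study withdrawal for an event that 5.1.6 treats as a reason to stop drug. The withdrawal reading conflicts with the treatment-policy estimand and the retention policy; the retention reading risks a recorded deviation.

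Its size is very small and rests on an assumed rate. With 1-3% of the active arm affected and full loss of benefit, the primary analysis would overstate the effect by at most about 0.8-2.5 mL, or 2-7% of the design standard error, and power would stay at or above 90%. The true rate may be near zero, in which case nothing measurable changes. The trial's conclusion would not be expected to change. This is a low-cost improvement in wording, not a threat to the result.

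**What to change.** Delete the infusion-reaction clause from the first bullet of the Protocol 4.3 list. State in 4.3 and 5.1.6 that a life-threatening infusion reaction mandates permanent discontinuation of study drug only, and that scheduled spirometry and HRCT continue to Week 48 unless consent is withdrawn or the Investigator judges the assessments themselves unsafe.

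The cost is wording in two sections and, for the few subjects affected, off-drug visits that are already in the schedule. Dosing still stops, and the general safety bullet still lets the Investigator withdraw any subject. With the clause gone, keeping such a subject in follow-up would no longer look like a missed withdrawal under SAP Table 1, so the SAP needs no change.
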